3.1 Hypothesis

The hypothesis of this prospective, observational study is that opioid tolerance occurs frequently in PICU patients, particularly those receiving ≥ 4 days of continuous fentanyl or morphine infusions.

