5.1 Analysis of Primary Endpoint

The primary endpoint for the MOTIF Study is the incidence of opioid tolerance among PICU patients receiving morphine or fentanyl infusions for analgesia and sedation. For the purposes of this study, opioid tolerance is defined by a doubling of the total daily opioid dose from the initiation of opioid therapy (0-24 hours) in the PICU. Tolerance can develop at any time during opioid therapy; therefore, as would be the case for an intention-to-treat analysis in a clinical trial, subjects who die or are discharged from the PICU will be included in the denominator for this endpoint, irrespective of number of days in PICU prior to death or discharge. We will examine the incidence of this endpoint 7 days and 14 days after initiation of morphine or fentanyl infusion therapy, in order to help determine appropriate parameters for future clinical trials. Rates of the primary endpoint will be summarized as proportions achieving tolerance by 7 days and by 14 days after opioid therapy initiation, together with appropriate confidence intervals.

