5.3 Explanatory Variables and Additional Analyses

These include demographic and clinical variables (such as age, gender, history of prior exposure, age at first exposure, duration of opioid therapy, use of concomitant medications, etc.) in order to identify possible risk factors for development of opioid tolerance during PICU therapy, and to generate hypotheses for future studies. In addition, since some opioid drugs are highly lipophilic (e.g. fentanyl) and others are not (e.g. morphine), we will calculate BMI and ideal body weight to evaluate the impact of increasing obesity on opioid tolerance.

In exploratory analyses, we will also assess rates of the primary and secondary endpoints according to other explanatory study variables. Factors examined in these analyses will include age, gender, history of prior exposure, age at first exposure, duration of opioid therapy, use of concomitant medications, and BMI. For continuous factors, categories will be defined using clinically appropriate cut-points, or quartiles of the observed data when such cut-points do not exist or are equivocal. Chi-squared tests or exact analogues will be used to compare proportions achieving the endpoint between subgroups. Logistic regression models will be used to assess factors that are independently predictive of tolerance, starting with candidate factors showing at least a weak statistical trend toward unadjusted association with the endpoint.

This study will be collecting information on other outcomes, for example, clinical status at PICU discharge and other clinical variables. The general strategy for analyses of other outcomes collected in this study will follow that specified for the primary and secondary study endpoints. Other binary or categorical outcomes such as PICU and hospital survival will be compared using chi-square tests or exact analogues. For other continuous outcome variables, summary statistics and box-plots will be used to investigate their distributions. Where indicated in order to ensure satisfaction of assumptions, we will either use transformations or non-parametric statistics.

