Univariate and multivariable regression analyses as described above (logistic for binary outcome, and linear regression for continuous outcomes appropriately transformed when necessary) will be used to assess the effects of covariates such as age, gender, and race. Tolerance-related parameters, such as time to doubling of the opioid dose, may be used as predictors in selected analyses. For outcomes recorded as integral days, such as time in PICU, we will also examine Poisson regression analyses using the SAS GENMOD procedure.

Exploratory repeated measures analyses will make use of the daily data elements collected in this study to assess patterns of opioid dosing across time, and examine factors associated with differences in such patterns. The general linear mixed model will be used for these analyses, to control for within-subject correlation of observations across time, and to appropriately model trajectories. Polynomial or spline models may be used as appropriate in these exploratory analyses to allow maximum flexibility in modeling observed patterns of dosing or response across time.

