5.4 Sample Size Estimates and Effect on Analysis

A conservative estimate of 450 subjects would be expected to yield a 95% confidence interval for proportion of opioid tolerance with precision ranging from 4-5%. We would expect 80% power to detect absolute differences in outcome rates of 14% or higher in exploratory comparisons between two subgroups of about equal size. In terms of ability to fit multivariable models, assuming an outcome rate of at least 25%, we would be able to fit models with up to 10 variables or factor levels, using the common "ballpark rule" of at least 10 events per factor in a logistic regression model. These analyses will refine the design of a randomized controlled trial and provide incidence estimates that are fairly accurate, in order to assist with the sample size calculations for a proposed intervention trial. In addition, clinical factors identified by the proposed multivariable analyses that are independently predictive of the primary outcome (or secondary outcomes) can be used for stratified enrollment in future clinical trials.

6 Accrual Projections and Duration of Study

At the CPCCRN centers from 2004-2006, there were 6,838 mechanically ventilated pediatric patients who did not require ECMO in the PICU. We propose enrollment of 450 subjects, a sample size that will permit estimation of the incidence of opioid tolerance with a precision of 4 to 5%. This sample will provide 80% power to detect outcome differences of 14% or higher in exploratory comparisons between subgroups of approximately equal size. The accrual period is anticipated to be up to 12 months.

7 Site Monitoring

Site monitors may visit each site at initiation, at a frequency to be determined by the DCC and National Institute for Child Health and Human Development (NICHD). The purposes of these visits are to help assure regulatory compliance at all sites, to improve the quality of data collection and management at each site, and to provide education to site coordinators and investigators (if needed). The site monitors may be hired by the DCC via a subcontract, and monitoring reports will be sent to the DCC.

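### Total duration of opioid therapy is tested as a risk factor for tolerance although it is the time at risk; concomitant drug use shares the fault if coded as any use during the stay

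*Protocol*

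**What the plan says.** Protocol section 5.1 treats tolerance as a yes/no event that may arise on any day of therapy. Children who die or leave the PICU "will be included in the denominator for this endpoint, irrespective of number of days in PICU". Results are proportions tolerant by 7 and by 14 days. Sections 4 and 4.3 end data collection at the last opioid dose, PICU discharge, death or day 14, whichever is earliest, so days at risk differ between children.

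Section 5.3 names the factors to be examined, including "duration of opioid therapy, use of concomitant medications, and BMI". For the comparison, "Chi-squared tests or exact analogues will be used to compare proportions achieving the endpoint between subgroups". Factors with at least a weak unadjusted association then become candidates for logistic regression. The hypothesis in section 3.1 singles out children with four or more "days of continuous fentanyl or morphine infusions". Section 5.4 would use factors found in the multivariable analyses to stratify enrolment in later trials.

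No time-to-event, person-day, landmark or time-updated method is given for tolerance. The mixed model in section 5.3 concerns dosing patterns. Time to doubling appears only as a possible predictor: "Tolerance-related parameters, such as time to doubling of the opioid dose, may be used as predictors in selected analyses".

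**The concern.** With the first day as reference, a child treated for one day cannot double the dose, and a child treated for 14 days has 13 days on which to do so. Total duration is thus the length of the observation window, fixed only at exit. A test of tolerance against it must show an association even if the risk on each day is the same for everyone. If tolerance itself prolongs therapy, the association grows further.

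Concomitant drug use can inherit the problem. One row per child requires the daily records to be collapsed. If they are collapsed to any use during the stay, longer stays give more chance both of use and of doubling, and use that starts after the doubling counts as exposure. Nothing in section 5.3 restricts use to day one or to the time before doubling.

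At stake is Specific Aim 2: whether a reported factor raises the risk of tolerance or only marks longer treatment.

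**Working it through.** **1. The plan's own figures.** Section 5.4 says "A conservative estimate of 450 subjects would be expected to yield a 95% confidence interval for proportion of opioid tolerance with precision ranging from 4-5" percent. The half-width is 1.96 × √(p(1−p)/450): 4.0% at p = 0.25 and 4.6% at p = 0.50, which agrees. It also claims "80% power to detect absolute differences in outcome rates of 14% or higher in exploratory comparisons between two subgroups of about equal size". At 43% versus 57% with 225 per group and two-sided 5% (the level is my assumption), power is 84.6%, so 14 points is slightly conservative. Finally, "assuming an outcome rate of at least 25%, we would be able to fit models with up to 10 variables or factor levels": 450 × 0.25 / 10 = 11.25, which agrees. The sample-size figures are not in dispute.

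**2. Assumptions.** The protocol gives no daily hazard, distribution of duration or drug-start rate. I assume a constant daily probability h of first doubling from day 2, unrelated to duration, and geometric durations T capped at 14 days. Nothing in this setting makes duration a cause of tolerance.

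**3. Tolerance by days of therapy.** P(tolerant | T) = 1 − (1 − h)^(T−1). With h = 0.05:

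| Days of therapy | 1 | 2 | 3 | 4 | 7 | 14 |
|---|---|---|---|---|---|---|
| Tolerant | 0% | 5.0% | 9.8% | 14.3% | 26.5% | 48.7% |

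**4. Four or more versus fewer days.** For median therapy of 4 days the daily stopping probability is 1 − 0.5^(1/4) = 0.159. Durations of 1, 2 and 3 days then have probabilities 0.1591, 0.1338 and 0.1125, in total 0.4054.

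- Fewer than 4 days: (0.1338 × 0.05 + 0.1125 × 0.0975) / 0.4054 = 4.4%.
- All children, averaging step 3 over the durations: 19.8%.
- Four or more days: (0.1977 − 0.4054 × 0.0436) / 0.5946 = 30.3%.
- Odds ratio: (0.303/0.697) / (0.0436/0.9564) ≈ 9.5.

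The same calculation gives 8.2 at h = 0.03 with median 3 days and 13.1 at h = 0.10 with median 6 days. In simulated studies of 450 (exponential durations with means of 4, 6 or 8 days before the cap, h of 5-10%), the chi-square for four or more versus fewer days was significant in every replicate.

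**5. A drug with no effect, coded as any use during the stay.** With h = 0.05, median therapy of 5 days and 1,500 simulated studies of 450:

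| Daily chance of starting the drug | Odds ratio | Significant by chi-square |
|---|---|---|
| 5% | 2.11 | 87% |
| 10% | 2.47 | 98% |
| 20% | 3.42 | 99.9% |

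Repetition of the 5% case also gave 83%, so the lower end is about 85%. In the scenarios of step 4 with starts of 10-20% per day, the rate was 93.5-100%.

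**6. What removes it.** In the step 4 simulations:

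- Duration added to the logistic model: the inert drug is significant in 5-12.5%.
- Person-day comparison, with use counted from the day after it starts: 3.5-6.2%.
- A baseline factor unrelated to duration, tested by the planned chi-square: 3.7-7.0%.

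The fault therefore lies in how exposure and time at risk are handled. Reverse causation was not simulated.

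**The case against.** The strongest reply is that section 5.3 calls these analyses exploratory and hypothesis-generating, and that the multivariable step deals with the problem. Duration is a named candidate and would pass the screen. Once it is in the model, most of the drug-use bias goes. Section 5.4 takes stratification factors from the multivariable analyses, not from the chi-square screen. This limits the size of the problem. But nothing requires duration to stay in the model, and its own coefficient would still measure time at risk.

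Any-use coding is an inference. The protocol speaks only of use, and section 4.2 (items 22 and 23) records day-one sedatives and analgesics, so baseline coding is possible. That point stands, and the drug result is conditional on it. Deferring to an analysis plan does not answer the point on duration, because the protocol itself names the factor and the tests.

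A reader might infer more than the text supports:

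- *The hypothesis is confirmed by construction.* Section 3.1 speaks of how often tolerance occurs, and no four-day test is specified. More cumulative tolerance with longer therapy is true as description; the error is to read it as a rise in daily risk.
- *False predictors will stratify later trials.* This is not shown for the multivariable models, and total duration is unknown at enrolment, so it could not be a stratification factor.
- *Time to doubling will be used to predict time in PICU.* Section 5.3 names no outcome for that predictor; time in PICU belongs to the next sentence, on Poisson regression.

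**Conclusion.** The point holds for total duration of opioid therapy. As planned, it appears as a strong risk factor with no change in daily risk: an odds ratio of about 8 to 13 for four or more versus fewer days, under assumed hazards of 3-10% and median durations of 3-6 days. The size depends on those inputs; the direction does not.

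For concomitant drugs it holds if use is coded over the whole stay: about 85-100% false positives unadjusted and about 5-12% with duration in the model, again under assumed inputs. Age, gender and BMI are affected only if related to duration. The 7- and 14-day proportions stand as descriptive cumulative incidences; the parallel that section 5.1 draws with intention to treat supports that denominator for description, not for relating the outcome to factors that accrue during follow-up.

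This should be fixed. The exploratory label keeps it from being critical, but these analyses are what serves Specific Aim 2.

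**What to change.** - Keep the 7- and 14-day proportions in section 5.1 as descriptive cumulative incidence.
- In section 5.3, replace the chi-square and logistic risk-factor analyses of tolerance with a person-day (discrete-time) logistic model or a cause-specific hazard model from Time 0. Use day of therapy as the time axis, and treat opioid stop, discharge and death as exits.
- Enter drug use either as use on day one or as a daily covariate lagged by one day, and say which.
- Drop total duration as a predictor of tolerance. Examine the four-day hypothesis by comparing the daily hazard before and from day 4, or by a landmark among children still on infusion at day 4.

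The cost is rewording section 5.3, modest programming, and the loss of a simple odds ratio for duration. The daily dose and drug records are already in the section 4.3 list. Item 19 there, on other sedatives and analgesics, literally refers to the first study day; it should be confirmed as meaning the day being recorded.

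### For the primary binary endpoint, continuous risk factors are grouped and compared by unordered chi-square, with no trend or continuous-scale test named, which costs power for graded effects under Specific Aim 2

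*Protocol*

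**What the plan says.** Protocol 5.3 lists seven factors to be related to the endpoints. Four are naturally continuous: age, age at first exposure, duration of opioid therapy and BMI. The other three are gender, prior exposure and concomitant medications. On the continuous ones it says: "For continuous factors, categories will be defined using clinically appropriate cut-points, or quartiles of the observed data when such cut-points do not exist". The same fallback applies where cut-points are unclear. Proportions reaching the endpoint are then compared between the groups by chi-square or exact tests.

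The multivariable step follows: "Logistic regression models will be used to assess factors that are independently predictive of tolerance, starting with candidate factors showing at least a weak statistical". What is meant is a trend in the unadjusted comparison, and no threshold for it is given. Later in 5.3, univariate and multivariable regression on covariates such as age is also planned, without saying whether age is continuous or grouped.

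For the continuous secondary endpoints, 5.2 adds correlations and scatterplots for continuous factors. Nothing comparable is named for the binary primary endpoint. Splines appear only for the repeated-measures analysis of dosing.

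On size, 5.4 claims "80% power to detect absolute differences in outcome rates of 14% or higher in exploratory comparisons between two subgroups of about equal size". For the model it says: "assuming an outcome rate of at least 25%, we would be able to fit models with up to 10 variables or factor levels", from a rule of "at least 10 events per factor in a logistic regression model".

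**The concern.** An unordered chi-square on four groups spends 3 degrees of freedom and takes no account of the order of the groups. If risk rises or falls steadily with the factor, that wastes information. Some of the questions are graded by nature: 5.3 itself wants to know what increasing obesity does to tolerance.

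The grouped comparison is also the only unadjusted test that 5.3 names ahead of the screen into the logistic model. A real graded factor that shows no trend there may never reach the multivariable stage. Finding such factors is one of only two specific aims, and 5.4 intends to use them for stratified enrolment in later trials.

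**Working it through.** **1. The plan's own figures.** Alpha is not stated; two-sided 5% is assumed.

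Two groups of 225, worst case 43% v 57%: power = Φ[(d − 1.96√(2p̄(1−p̄)/n)) / √((p₁q₁+p₂q₂)/n)] = Φ[(0.14 − 1.96×0.0471)/0.0467] = Φ(1.02), about 84.6%. With continuity correction it is 82.2%. The difference detectable with 80% power is 13.2 points, or 13.6 corrected. The stated 14 points is sound and slightly conservative.

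Model size: 450 × 0.25 = 112.5 events, and 112.5/10 = 11.25. The stated 10 is also sound.

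**2. Cost of grouping for a graded effect.** Inputs: N=450 and a 25% rate (5.4). Assumed: a normal factor and a logit-linear effect. Power comes from the noncentral chi-square distribution:

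- continuous term, 1 df: λ = N·[mean(x·p)]² / [p̄(1−p̄)·mean(x²)]
- quartiles, 3 df: λ = N·mean[(p_q − p̄)²] / [p̄(1−p̄)]

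Example, slope 0.30 per SD (odds ratio 1.35): the quartile rates are 18.3%, 22.8%, 26.5% and 32.4%. Then λ is about 7.35 for the continuous term and 6.37 for quartiles. The grouping itself loses little; most of the cost comes from spending 3 df (critical value 7.81 instead of 3.84).

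| Slope per SD (OR) | Test level | Continuous, 1 df | Quartiles, 3 df | Loss (points) | Trend over quartiles, 1 df |
|---|---|---|---|---|---|
| 0.25 (1.28) | 5% | 62% | 40% | 22 | 56% |
| 0.30 (1.35) | 5% | 77% | 54% | 23 | 71% |
| 0.35 (1.42) | 5% | 88% | 69% | 19 | 83% |
| 0.25 | p<0.20 | 84% | 67% | 17 | 79% |
| 0.30 | p<0.20 | 92% | 79% | 13 | 89% |
| 0.35 | p<0.20 | 97% | 88% | 9 | 95% |

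Simulation with 1,500 replicates per setting agrees at 5%: 63% v 41%, 76% v 53% and 88% v 67%. A median split does little better than quartiles (58% at slope 0.30), so a two-group clinical cut-point near the median would not remove the loss.

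**3. Sensitivity at 5%.**

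- Uniform factor, continuous test at 80% power: quartiles 61.5%, a loss of about 19 points.
- An effect that gives the plan's own 14 points between halves: 99.0% v 93.5% (normal factor, 25% rate) to 92.8% v 80.3% (uniform factor, 50% rate), a loss of about 6 to 13 points.
- Strongly skewed (log-normal) factor with an effect linear on the raw scale: a loss of about 26 to 41 points.
- U-shaped effect: quartiles 14% to 32%, linear term 5%. Here quartiles win.

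**4. Term count.** Four factors as quartiles need 4 × 3 = 12 indicators. With one term for each of the other three this is 15, or 112.5/15 = 7.5 events per term. Kept linear, the seven factors take 7 terms, or 112.5/7 = 16 events per term.

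**The case against.** The best reply is that 5.3 leaves more open than a quick reading suggests. Grouping is described in the setting of reporting rates, and rates need groups. Clinical cut-points come first and quartiles are the fallback. Univariate logistic regression on age is planned with its form unstated. The screen asks only for a weak trend, so 5% is too strict a level for judging it. The moderate effects in the table amount to about 9 to 10 points between halves for slopes 0.30 and 0.35, below the 14 points that the plan aims for. The analyses are labelled exploratory, and the primary incidence estimate is untouched.

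Most of this stands, and it rules out three stronger conclusions that a reader might draw:

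- **That grouping costs a flat 20 points.** This is roughly right for a moderate graded effect tested at 5%. It is too high for a looser screen or for the plan's own effect size, and the sign reverses for U-shaped effects.
- **That the primary endpoint is never analysed on the continuous scale.** The planned regression on age may be continuous; the protocol does not say.
- **That the plan breaks its own limit of 10.** The statement "we would be able to fit models with up to 10 variables or factor levels" already counts levels and caps the fitted model. The count of 15 needs all four continuous factors coded as quartiles and fitted together with the other three, after a screen that may drop some. The document states none of this.

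The reply does not remove the main point. The test that 5.3 does name for the binary endpoint ignores order, and it sits directly before the selection of factors.

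**Conclusion.** The point holds as a cheap improvement to a stated method; no figure in the plan is in error. Under a graded log-linear effect with 450 subjects, a 25% rate and a normal factor, quartile chi-square testing loses about 19 to 23 points of power at two-sided 5% for slopes of 0.25 to 0.35 per SD, and about 9 to 17 points at p<0.20. Both test levels, the shape of the effect and the factor's distribution are assumptions. Larger effects lose less, and non-monotone effects can favour quartiles. The 14-point and 10-level statements in 5.4 stand.

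**What to change.** In 5.3, test each continuous factor for the primary endpoint on its continuous scale in logistic regression, and use that test for the screen. Use a linear term, or a 3-knot restricted cubic spline where non-linearity is plausible, such as for age; the spline also guards against the U-shaped case. Keep clinical categories or quartiles for the descriptive tables of rates. If grouped testing is to stay, use at least a 1-df trend test across the ordered groups, which recovers most of the loss (71% against 54% for the unordered test and 77% for the continuous term at slope 0.30).

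No change to the figures in 5.4 is needed.

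The cost is a change of wording, with no new data. The small downside is that an odds ratio per unit, or a spline curve, is less immediate to a clinical reader than a rate by group, which is why the descriptive tables should stay.

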4.1 Definitions

- **Analgesia:** the reduction or absence of the sense of pain without loss of consciousness, as reported by the patient, or judged clinically from the patients behavior or physiological responses
- **Sedation:** a pharmacologically produced depressed level of consciousness associated with reduced anxiety, stress, and excitement

- First study day: the period from the time that the initial dose of opioid is received in the PICU up to 23:59 hours on that day
- **Subsequent study days:** each calendar day starting at midnight (00:00 hours) and ending at 23:59 hours after the completion of the first study day (as defined above) during which the enrolled subject is an inpatient in the PICU
- **Ventilated day:** PICU day during any part of which the child requires mechanical ventilation support greater than chronic baseline requirements (out of the hospital), provided by endotracheal tube, tracheostomy, laryngeal or face mask
- **Invasive procedure:** Any procedure that breaks the skin barrier or mucous membrane barrier or involves the placement of a medical device (catheter, probe, electrode, drain, prosthetic, or anything else) into a body orifice or body cavity, other than momentary suctioning of the nose, mouth, endotracheal tube, or tracheostomy tube.
- **Opioid tolerance:** the need for increasing doses of opioid drugs in order to maintain the same pharmacological effects as those seen at the initiation of therapy. For the purposes of this study, opioid tolerance is clinically defined as a doubling of the total daily opioid dose (including infusions and boluses) as compared to the total daily opioid dose required during the first 24 hours of opioid therapy, in order to maintain adequate analgesia and sedation
- **Regularly scheduled opioids:** the subject receives opioid drugs daily, given at regularly scheduled intervals. In response to specific symptoms or signs, if the subject has received more than one opioid dose per day, on more than three days during the past week, or a total of more than six opioid doses in the past one week, then they will be considered equivalent to those receiving regularly scheduled opioids.
- **Chronic opioid treatment:** if the subject has received scheduled regular opioids (as defined above) for more than one week, they will be classified as receiving chronic opioid treatment.

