4.3 Subsequent Daily Data Elements

Study Day One is the day of enrollment, beginning at the time of the first morphine or fentanyl administration in the PICU, and ending at 23:59 on that day. Each subsequent study day is defined as midnight (00:00) to 23:59. On each subsequent day (not study day one), the following data elements

Sedative Drugs and Components Sedative Drugs Answer Ketamine Yes or No Propofol Yes or No Chloral hydrate Yes or No Chlorpheniramine Yes or No Clonazepam Yes or No Diazepam Yes or No Droperidol Yes or No Etomidate Yes or No Yes or No Haloperidol Yes or No Hydroxyzine Methohexital Yes or No Yes or No Pentobarbital Phenobarbital Yes or No Promethazine Yes or No Yes or No Thiopental Yes or No Other (specify)

Table 1: Sedative agents.

Analgesic Drugs and	Components
Analgesic Drugs	Answer
Dexmedetomidine	Yes or No
Acetaminophen	Yes or No
Ibuprofen	Yes or No
Acetylsalicylic acid	Yes or No
Alfentanil	Yes or No
Buprenorphine	Yes or No
Butorphanol	Yes or No
Clonidine	Yes or No
Codeine	Yes or No
Dextromethorphan	Yes or No
Hydromorphone	Yes or No
Ketorolac	Yes or No
Meperidine	Yes or No
Methadone	Yes or No
Nalbuphine	Yes or No
Oxymorphone	Yes or No
Remifentanil	Yes or No
Tramadol	Yes or No
Other (specify)	Yes or No

Analgesic Drugs and Components

Table 2: Analgesic agents.

will be collected. This daily data collection will continue through Study Day 14, discontinuation of opioid therapy, death, or PICU discharge, whichever occurs earliest.

- 1. Date of data collection
- 2. Study day number (2 to 14)
- 3. Weight (kg) last measured or estimated weight
- 4. Was morphine or fentanyl infusion weaned (decreased) in the past 24 hours? (Yes or No)
- Was morphine or fentanyl infusion discontinued in the past 24 hours? (Yes or No) If yes to this question,
 - (a) Was morphine or fentanyl infusion restarted in the past 24 hours? (Yes or No)
 - (b) Were intermittent opioid doses started in the past 24 hours? (Yes or No)
- 6. Were muscle relaxants used in the past 24 hours? (Yes or No)
- 7. Were physical restraints used in the past 24 hours? (Yes or No)
- 8. Did inadvertent or unplanned dislodgement of an endotracheal tube occur in the past 24 hours? (Yes or No)
- 9. Did inadvertent or unplanned dislodgement of a central venous line occur in the past 24 hours? (Yes or No)
- 10. Did inadvertent or unplanned dislodgement of an arterial line occur in the past 24 hours? (Yes or No)

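### Section 5.3 lets time to doubling enter ordinary regression as a predictor with no outcome excluded; if the outcome is PICU stay, an association appears even when there is none

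*Protocol*

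**What the plan says.** Section 5.3 (Explanatory Variables and Additional Analyses) first gives the regression models: "logistic for binary outcome, and linear regression for continuous outcomes appropriately transformed when necessary". It then says: "Tolerance-related parameters, such as time to doubling of the opioid dose, may be used as predictors in selected analyses". The sentence after that reads: "For outcomes recorded as integral days, such as time in PICU, we will also examine Poisson regression analyses using the SAS GENMOD procedure". Earlier in the same section, PICU and hospital survival are listed among the other outcomes. Section 5 mentions neither a landmark analysis nor a time-dependent covariate. Its mixed models are for dosing patterns over time.

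Other sections settle when a doubling can be seen:

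- Section 5.1: "opioid tolerance is defined by a doubling of the total daily opioid dose from the initiation of opioid therapy (0-24 hours) in the PICU".
- Section 4.1 counts later study days as calendar days "during which the enrolled subject is an inpatient in the PICU".
- Section 4.3: "This daily data collection will continue through Study Day 14, discontinuation of opioid therapy, death, or PICU discharge, whichever" comes first.
- Section 5.1, on children who leave early: "subjects who die or are discharged from the PICU will be included in the denominator for this endpoint, irrespective of number of days in PICU".

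**The concern.** Time to doubling is learned during follow-up. It exists only for children who stayed long enough, on opioids, to double, and it can never be longer than the stay. A linear, logistic or Poisson model with a fixed covariate treats it as known at the start. When the outcome is stay, the predictor is then partly a measure of the outcome. This is immortal-time bias.

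Tolerance yes/no is not named in the sentence, but it is a tolerance-related parameter and has the same problem. The 5.1 rule keeps early leavers in the denominator, which suits an incidence estimate. Reused as a predictor, the same classification places short stays in the non-tolerant group because they were short.

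At stake is a possible false statement that tolerant children stay longer, or that later doubling goes with longer stay. Section 2.3 already cites prolonged hospital stays in children with opioid tolerance, so an artefact in that direction would look like confirmation.

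**Working it through.** **The plan's own figures.** The protocol gives no figure for this analysis. Its sample-size figures in 5.4 reproduce and are not in dispute. The 95% half-width is 1.96 × √(p(1−p)/450), which is 4.0% at p = 0.25 and 4.6% at p = 0.5, against the stated 4-5%. With 225 per group, 80% power near p = 0.5 needs a difference of 13.2 points (about 13.6 with continuity correction), against the stated 14% or higher.

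**Mechanism.** Suppose doubling has a constant hazard h per day from day 1, unrelated to stay L, with opioids running to discharge. The chance that a doubling is seen is

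P(seen | L) = 1 − exp(−h × (min(L, 14) − 1)).

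With h = 0.05 (assumed):

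- L = 4 days: 1 − exp(−0.15) = 0.14
- L = 7 days: 1 − exp(−0.30) = 0.26
- L = 14 days: 1 − exp(−0.65) = 0.48

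The hazard is the same for every child, yet the chance of being classed tolerant more than triples from a 4-day to a 14-day stay. Among those who double on day t, only stays of at least t remain, so mean stay rises with t.

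**Simulation under no effect.** The inputs were 450 children (5.4) and observation up to day 14, end of opioids or discharge (4.3). Assumptions: log-normal stay with log-SD 0.7, and a doubling time independent of stay. There were 300 runs per row (200 for Cox), testing at nominal 5%. Poisson standard errors are robust, so over-dispersion is not the cause.

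| Median stay, hazard | Doubling seen | Mean stay, tolerant vs not | False stay ratio | Rejects: yes/no | Rejects: time to doubling | Stay ratio per day of later doubling | Cox, time-dependent | Day-4 landmark |
|---|---|---|---|---|---|---|---|---|
| 4 d, 0.08 | 24.4% | 8.1 vs 4.8 | 1.71 | 100% | 100% | 1.12 | 6.0% | 7.7% |
| 6 d, 0.05 | 24.2% | 11.1 vs 7.2 | 1.54 | 100% | 99.7% | 1.08 | 8.0% | 3.3% |
| 6 d, 0.08 | 34.7% | 10.9 vs 6.7 | 1.62 | 100% | 100% | 1.08 | 5.5% | 6.3% |
| 8 d, 0.05 | 30.0% | 13.7 vs 9.5 | 1.45 | 99.7% | 98.0% | 1.07 | 5.0% | 3.0% |
| 10 d, 0.05 | 33.8% | 16.1 vs 11.8 | 1.36 | 98.3% | 94.0% | 1.05 | 4.0% | 6.0% |
| 8 d, 0.08, opioids stop at 40-100% of stay | 32.5% | 14.5 vs 8.9 | 1.62 | 100% | 99.0% | 1.08 | not run | 11.7% |

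Linear regression on log stay rejected in 100% of runs in every row, for both predictors.

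Monte Carlo error: √(0.05 × 0.95/200) = 1.5 points for Cox and √(0.05 × 0.95/300) = 1.3 points for the landmark. The first five rows are therefore compatible with about 5% for both remedies. The 11.7% is not: (11.7 − 5)/1.3 is about 5 standard errors. In that row the landmark kept children whose opioids had already stopped.

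**Other assumptions.**

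- Gamma stay (mean 6, 8 or 12 days, shape 1 to 3), about 20-27% doubling, 400 runs. Time to doubling: Poisson 98-100%, over-dispersion-corrected Poisson 79-100%, linear on log stay 99-100%. Tolerance yes/no: 95-100%, ratios 1.2-2.1. Day-4 landmark: 4-7%.
- Log-normal stay with median 4, 6 or 10 days, hazard 0.06, opioids ending early or not, stay cut at day 14 or not. Fixed-predictor models: 99-100%, ratios 1.24-1.61. Day-4 landmark restricted to children still on opioids: 4-7%.

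**The case against.** The strongest reply is that the protocol does not commit to this analysis. The sentence says the parameters may be used, in selected analyses, and names no outcome. The Poisson sentence that follows is a general remark about outcomes counted in days, so pairing the two is an inference from their position. This stands, and it limits the weight of the point. It does not remove it: the text allows the predictor without restriction, and stay and survival are among the outcomes offered in the same section.

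A reader might also infer that the trial will report that tolerance prolongs stay, that it tests a null hypothesis about tolerance and stay, or that such a result would shape the future intervention trial. The documents support none of these. The hypothesis and aims concern the frequency of tolerance and its risk factors. Section 5.4 carries forward incidence estimates and predictors of the primary or secondary outcomes, so there tolerance is the outcome.

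It can be said that the choice of method belongs in a statistical analysis plan. Missing detail would be no finding. Here the protocol gives a permission that leads to a wrong result if followed for stay.

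Finally, the data list may not hold the full stay. Section 4.4 records the day, time and reason of study exit, but no PICU discharge date for children who exit because opioids stopped or day 14 ended. That is correct, and it affects the protocol's own time-in-PICU model equally. Cutting stay at day 14 in the simulations did not remove the false association.

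**Conclusion.** The point holds as a conditional one. Section 5.3 permits a predictor that, entered as a fixed covariate for PICU stay, gives a false association by construction. The false rejection rate is about 80-100% at nominal 5%, with false stay ratios of about 1.2-2.1 for tolerant versus not and, in the tabulated runs, 5-12% longer stay per day of later doubling. The direction follows from the definitions. The sizes rest on assumed stay distributions and hazards, but the association appeared in every scenario tried.

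For death as the outcome, a reader might expect the bias to run the other way, since children who die early cannot double. That was not computed, and no size is claimed.

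The analysis is optional and exploratory. The primary endpoint, secondary endpoints and sample size are untouched. A change of wording is worthwhile because it is cheap and the error is predictable.

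**What to change.** Replace the sentence in 5.3 with:

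> Tolerance-related parameters will be related to later outcomes such as PICU stay or survival only by a landmark analysis (status or dose ratio reached by a fixed study day, among children still in the PICU and still on opioids on that day, with the outcome counted from that day) or with tolerance as a time-dependent covariate; time to doubling will not be entered as a fixed predictor of these outcomes.

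The condition of still being on opioids matters, as the 11.7% row shows. The time-dependent model was checked only with opioids running to discharge, so it too should account for current opioid status.

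Cost: one sentence and modest changes to code. The landmark loses children who leave or stop opioids before the chosen day, so there are fewer tolerant children and wider intervals.

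Data: add the PICU discharge date to the 4.4 exit elements for children who leave the study for another reason. Section 4 requires a protocol amendment for an added element. Without it, stay can be analysed only as censored at study exit, and censoring when opioids stop is unlikely to be independent of discharge.
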